Dual antiplatelet therapy (DAPT) with aspirin and a P2Y₁₂ receptor inhibitor represents the standard of care for the long-term secondary prevention of atherothrombotic events in patients with myocardial infarction (MI) [1]. Clopidogrel is the most widely used P2Y₁₂ receptor inhibitor and the use of DAPT with aspirin and clopidogrel has consistently demonstrated to reduce the risk of thrombotic recurrences in patients with acute coronary syndrome (ACS) [2]. However, clopidogrel is a prodrug characterized by high interindividual response variability [3]. The novel P2Y₁₂ receptor inhibitors prasugrel and ticagrelor are characterized by more prompt, potent, and predictable antiplatelet effects compared with clopidogrel and are associated with a greater reduction of ischemic events in ACS patients, at the expense of an increase in major bleeding [4,5]. However, despite adequate cyclooxygenase-1 (COX-1) and ADP P2Y₁₂-receptor blockade, rates of ischemic recurrences remain high, which may be in part due to the fact that other platelet signaling pathways, such as thrombin-induced platelet aggregation, continue to be activated and can thus contribute to thrombus formation [2,6,7]. In particular, the serine protease thrombin is one of the most potent platelet activators and the surface of activated platelets is the main source of circulating thrombin, especially following an ACS [6-8]. Vorapaxar is a novel, orally active, highly selective, competitive and slowly reversible protease-activated receptor (PAR)-1 inhibitor, which exerts potent inhibition of thrombin-mediated platelet activation and aggregation [9,10]. After oral administration vorapaxar is rapidly absorbed with high bioavailability (>90%) and is metabolized by cytochrome P450 (CYP) 3A4. Pharmacokinetic studies have shown that vorapaxar has a dissociation half-life as long as 20 hours which leads to consistent pharmacodynamic (PD) effects [9,10]. Importantly, there is an

interplay between purinergic and thrombin mediated platelet signaling pathways which may result in enhanced P2Y₁₂ inhibition when vorapaxar is added to DAPT [11].

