8. On treatment with any antiplatelet agent other than aspirin, prasugrel and ticagrelor in the past 14 days.
9. Creatinine clearance <30 mL/minute.
10. Platelet count <80x10⁶/mL
11. Hemoglobin <10g/dL
12. Hemodynamic instability

13. Pregnant females [women of childbearing age must use reliable birth control (i.e. oral contraceptives) while participating in the study].

Research Design

The proposed investigation will be a prospective, randomized, parallel-design, open label, PD study conducted in a real world clinical setting of post-MI patients. Patients will be required to be on DAPT for at least 2 weeks before randomization. Although vorapaxar is approved for use irrespective of the timing of the MI, the rationale for including patients after 2 weeks is that, given the negative results of the clinical trial with vorapaxar in the acute phase of ACS, it may be reasonable to wait until patients have been stabilized after their index MI [18]. The rationale for the exclusion of elderly patients (aged >75 years) and patients with a low body weight (<60 kg) is that prasugrel is generally not recommended in these patient populations [1,2].

[figure not shown]
The study will be performed at the University of Florida Health Science Center at UF Health Jacksonville - Division of Cardiology. Patients will be recruited in the Cardiology Clinics of our institution and will be screened by Cardiology Research staff, who will verify that all candidates meet inclusion and exclusion criteria. Results from blood tests performed within the last 90 days will be considered valid for screening purposes. If these are not available, a blood sample will be collected for the screening phase. Although the study has an open-label design, laboratory personnel performing PD testing will be blinded to treatment assignment.

Patients on DAPT with aspirin and prasugrel/ticagrelor as part of their standard of care for at least 2 weeks and who are meeting study entry criteria will be randomly assigned in a 1:1:1 fashion to one of the following 3 treatment regimens: 1) DAPT (aspirin and prasugrel/ticagrelor) plus

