vorapaxar 2.5mg od; 2) prasugrel/ticagrelor plus vorapaxar 2.5mg od; 3) continue DAPT with aspirin and prasugrel/ticagrelor. Randomized treatment will be administered for 30 ± 3 days; prasugrel and ticagrelor will be administered at their standard maintenance dose (10mg od and 90mg bid, respectively). Randomization will be stratified according to type of P2Y₁₂ inhibitor, in order to include at least 35% of patients on prasugrel. The rationale for predicting a higher number of randomized patients on ticagrelor derives from the more broad clinical indications of ticagrelor compared with prasugrel. Patient who entered the study before being on DAPT for 2 weeks will be required to complete 2 weeks of DAPT with aspirin and prasugrel/ticagrelor before randomization.

Blood sampling for PD testing will be conducted at 3 time-points: a) baseline (while patients will be on standard DAPT prior to initiating randomized treatment); b) after 7-10 days of randomized study treatment; c) after 30 ± 3 days of randomized study treatment. At each time point, blood will be collected before the morning dose of prasugrel/ticagrelor and vorapaxar, in order to measure trough levels of platelet inhibition. During study treatment in-hospital major adverse cardiac events (death, MI, stroke, and urgent revascularization procedures) and serious adverse events (bleeding and other adverse events) will be collected. Bleeding will be defined by the BARC (Bleeding Academic Research Consortium) definition [19].

After study completion, patients will resume antiplatelet treatment regimen at the discretion of the treating physician. A flow diagram of the study design is illustrated below.

Laboratory assessments

Peripheral venous blood samples (20 mL) will be drawn through a short venous catheter inserted into a forearm vein and collected in citrate, EDTA, and serum tubes as appropriate for assessments. The first 2-4 mL of blood will be discarded to avoid spontaneous platelet activation. Blood sampling for PD will be performed at 3 time points as indicated above in the study design section. Various PD assays will be performed as described below. Given the potential interplay between PAR-1 and P2Y₁₂ mediated signaling, assessments specific for both pathways will be conducted [11]:

1. Light transmittance aggregometry (LTA)
2. Thrombelastograph Coagulation Analyzer TEG 6s Series system (CORA[®] system)
3. Whole blood vasodilator-stimulated phosphoprotein (VASP)
4. Serum thromboxane B2

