4) Serum thromboxane B2: The concentration of serum thromboxane B2 (TXB2) will be measured by using the TXB2 EIA kit (Cayman Chemical Company, Ann Arbor, MI) according to the instructions of the manufacturer, as previously described [24]. Briefly, samples will be diluted with EIA buffer to bring their concentrations within the range of the standard curve. No other purification will be performed on any of the samples. A standard curve will be established by serial dilution of TXB2 between 1000 pg/mL and 7.8 pg/mL using EIA buffer as the matrix. The concentration of TXB2 in the samples will be calculated from a logistic 4-parameter fit of the standard concentrations versus percentage bound/maximum bound.

Study endpoints and sample size calculation

The primary end point of our study is the comparison of CAT-induced MPA between DAPT and DAPT plus vorapaxar after 30 ± 3 days of treatment. We hypothesize that adjunctive vorapaxar will result into a significant reduction of platelet aggregation. Assuming a 10% absolute reduction in CAT-induced MPA with a common standard deviation of 13%, 37 patients per group will be needed to detect a significant difference between DAPT and DAPT plus vorapaxar with a 90% power and 2-sided $\alpha=0.05$. Considering a possible 30-35% rate of invalid results due to hemolysis or drop-out and the three arms of treatment up to 146 patients will need to be randomized. Since there are no preliminary data in this particular setting, the sample size of our study was calculated based on previous data of vorapaxar in addition to DAPT with aspirin and clopidogrel [21]. This approach is in agreement with recommendations for pilot investigations [25].

Our secondary outcome will be the comparison of CAT-induced MPA between vorapaxar in addition to a new generation P2Y₁₂ receptor inhibitor (prasugrel or ticagrelor) and vorapaxar in addition to standard DAPT (aspirin and prasugrel/ticagrelor). We hypothesize that stopping aspirin will not lead to significant differences in CAT-induced MPA after 30 ± 3 days of treatment.

Other objectives will include the comparisons among the 3 groups of all PD parameters measured by multiple assays at every time point, as well as intragroup comparisons of PD parameters in order to evaluate the variability over time of vorapaxar PD effects, as well as how PD measures will be affected by aspirin withdrawal.

Statistical analysis plan

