Categorical variables will be expressed as frequencies and percentages. Continuous variables will be presented as mean \pm SD or median [IQR]. Continuous variables will be analyzed for normal distribution with the Kolmogorov-Smirnov test. Comparisons between categorical variables will be performed using two-tailed Fisher's exact test or the Pearson's chi-square test. Student's t test, Mann-Whitney U-test and Wilcoxon test will be used to compare continuous variables when appropriate. An analysis of covariance (ANCOVA) method with a general linear model, using baseline variables significantly different between groups as covariates, will be used to evaluate the overall difference between groups and all between-groups comparisons, in line with other PD studies [23]. Analysis of variance (ANOVA) will be used to evaluate intragroup comparisons. A 2-tailed p value of < 0.05 is considered to indicate a statistically significant difference for all the analyses performed. Statistical analysis will be performed by our group using SPSS v22.0 software (SPSS Inc. Chicago, IL).

Publication Strategy/Additional Information

Study subjects will be identified first (months 1-24): we expect to enroll approximately 5-6 subjects monthly and complete enrollment in 24 months (total: 126 subjects enrolled). Months 25-26 will be implied for statistical analysis and months 27-28 for manuscript preparation. We intend to present data at a major scientific meeting at completion of the study.

We anticipate no major problems with the described protocol since the approach is a straight forward prospective study and is based on well-established methods. However, since there is limited experience with vorapaxar to define platelet function, variability may be higher than expected and we cannot currently perform a detailed sample size calculation. We anticipate adding this to the protocol after inclusion of the study population has been completed. If the sample size after one year is estimated to be too small, additional patients will be included. This approach is in agreement with recommendations for pilot investigations [25].

Possible Discomforts and Risk

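### Change over time in vorapaxar's effect is assigned to within-arm comparisons that do not subtract the concurrent DAPT arm's change, so background drift may be mistaken for, or may mask, a change in drug effect

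*Combined protocol and SAP*

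**What the plan says.** The section on study endpoints and sample size lists two kinds of analysis in one sentence under its other objectives. The first is "comparisons among the 3 groups of all PD parameters measured by multiple assays at every time point". The second is "intragroup comparisons of PD parameters in order to evaluate the variability over time of vorapaxar PD effects"; the sentence also mentions the consequences of stopping aspirin.

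The Statistical analysis plan gives each kind a method. For within-arm work: "Analysis of variance (ANOVA) will be used to evaluate intragroup comparisons". For between-arm work the method is ANCOVA, with covariates picked by a significance rule: "using baseline variables significantly different between groups as covariates, will be used to evaluate the overall difference between groups and all between-groups comparisons". A two-tailed threshold of 0.05 applies to every analysis.

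Under Research Design, arm 1 is DAPT plus vorapaxar, arm 2 drops aspirin, and arm 3 is to "continue DAPT with aspirin and prasugrel/ticagrelor". The schedule is the same for all arms: "Blood sampling for PD testing will be conducted at 3 time-points", namely baseline, day 7-10 and day 30 ± 3.

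No arm-by-visit term, cross-arm repeated-measures model or between-arm comparison of change appears anywhere.

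**The concern.** Vorapaxar's effect at a visit is the difference between having it and not having it at that visit. How the effect varies over time is therefore the change in that difference. Change within arm 1 is a different quantity: it adds whatever else moves between the two visits, such as recovery after the infarction or assay drift. Running the ANOVA properly as a repeated-measures analysis would not help, because the quantity estimated stays the same. Aspirin is constant in arms 1 and 3, so the point does not depend on the aspirin-withdrawal question.

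At stake is a statement that the effect grows or wanes between day 7-10 and day 30 when it is constant, or a real change hidden by drift in the other direction. The DAPT arm would show any drift common to the arms at no extra cost, but the rule given for this objective does not use it.

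**Working it through.** **Inputs from the documents** (section on study endpoints and sample size): difference 10 MPA points, SD 13, 37 per group, 90% power, two-sided 0.05.

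**Assumptions, not in the documents:** correlation rho between the day 7-10 and day 30 values in the same patient, 0.3 to 0.8; drift of 0, 2, 3 or 5 points, identical in arms 1 and 3; constant vorapaxar effect. SD 13 is the planning SD for a between-arm comparison, used here at each visit.

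**The plan's own figure.** n = 2 × 13² × (1.960 + 1.282)² / 10² = 35.5, so 36 by the normal approximation. The t-test solution is 36.5, so 37. The plan's 37 is reproduced. The documents give no figure for the comparisons over time.

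**Standard errors.** SD of a patient's change = 13 × √(2(1 − rho)). Within-arm SE = that SD / √37. SE of the difference in change (arm 1 minus arm 3) = √2 times the within-arm SE. At rho 0.6, the SD of change is 13 × √0.8 = 11.63, the within-arm SE is 11.63 / 6.083 = 1.91, and the contrast SE is 2.70.

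**False positives.** Chance that a paired test of day 30 against day 7-10 within arm 1 gives p < 0.05 (noncentral t, 36 df, noncentrality = drift / within-arm SE):

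| rho | within-arm SE | no drift | 2 points | 3 points | 5 points |
|---|---|---|---|---|---|
| 0.4 | 2.34 | 5% | 13% | 24% | 55% |
| 0.6 | 1.91 | 5% | 17% | 33% | 72% |
| 0.8 | 1.35 | 5% | 30% | 58% | 95% |

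In 20,000 simulated trials per case, with rho 0.3, 0.5 and 0.7 and drift 0, 2, 3 and 5, the difference-in-change test rejected in about 5% of trials throughout. That follows from assuming equal drift in both arms.

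**Would reading the arms side by side do?** With 3 points of common drift, the same simulations found arm 1 significant and DAPT not significant in 17%, 20% and 25% of trials (rho 0.3, 0.5, 0.7), although the drug effect did not change.

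**Precision of the alternative.** Change detectable with 80% power = (1.960 + 0.842) × SE, with 37 per arm:

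| rho | within-arm | contrast |
|---|---|---|
| 0.3 | 7.1 | 10.0 |
| 0.5 | 6.0 | 8.5 |
| 0.7 | 4.6 | 6.6 |

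**The case against.** The strongest reply is that the controlled information is already planned. Comparing the three groups at every time point yields vorapaxar against DAPT at day 7-10 and at day 30, and the within-arm rule, read naturally, covers the DAPT arm too. A reader might infer that the randomised control is thrown away for this objective. The documents do not support that: both controlled differences will be available. What stands is narrower. The change-over-time question is given to the within-arm comparisons, and two visit-wise differences reported separately carry no standard error or interval for their difference.

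The second reply is that nothing shows drift exists. This is largely right. A reader might infer that drift will occur and will be reported as a changing drug effect. The documents contain no drift figure. Entry requires at least 2 weeks of DAPT, no bleeding or ischemic events since the infarction, and an infarction within 12 months, so an infarction only weeks old is one end of the range. The stated reason for delaying entry, "it may be reasonable to wait until patients have been stabilized after their index MI", is a step against instability and not evidence of it. The remark that "the surface of activated platelets is the main source of circulating thrombin, especially following an ACS" is general biology and says nothing about MPA between these two visits. A drift of 5 points would be half of the whole assumed drug effect. Still, none of this establishes that drift is zero, and a concurrent control removes the need to assume it.

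Third, arm 3 does not capture all background. Its patients take no vorapaxar, so changing adherence to vorapaxar stays in the proposed contrast. Only drift common to the arms is removed.

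Finally, the contrast is imprecise. At correlation 0.5 it detects about 8.5 points with 80% power, against a full expected effect of 10. That is a reason to report an estimate with its interval. It does not make the more precise within-arm figure an answer to the stated question.

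**Conclusion.** The point holds in a limited form. For one of the other objectives, the plan assigns a question about drug effect over time to comparisons that cannot separate it from common background change, and it specifies no between-visit contrast of the arm differences.

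The harm is conditional. It is nil if there is no drift; under common drift of 2 to 5 points and correlations of 0.4 to 0.8, the false-positive rate runs from about 13% to 95%. Those drifts and correlations are assumptions, so the range shows sensitivity and is not a forecast.

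The primary and secondary comparisons are between randomised arms at day 30 and are untouched. The matter is a modest but worthwhile correction to the analysis plan.

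**What to change.** In the Statistical analysis plan, replace the within-arm rule for this objective with one sentence: the change in vorapaxar's effect is (arm 1 minus arm 3 at day 30) minus (arm 1 minus arm 3 at day 7-10), estimated with a 95% CI from a repeated-measures model with arm, visit, arm-by-visit and the baseline value of the parameter. Keep within-arm changes as description, without inference about the drug. State that a non-significant contrast is not evidence that the effect is stable, and interpret the interval instead.

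No new samples, visits or patients are needed. The cost is precision: the standard error is 1.41 times larger, about 2.7 against 1.9 points at correlation 0.6. Changing adherence to vorapaxar remains part of the estimate, and the report should say so.

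### Covariates for the ANCOVA are picked by baseline significance tests, so baseline CAT-induced MPA and the P2Y12-inhibitor stratum will usually be left out and precision lost

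*Combined protocol and SAP*

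**What the plan says.** The primary endpoint (Study endpoints and sample size calculation) is the "comparison of CAT-induced MPA between DAPT and DAPT plus vorapaxar after 30 ± 3 days of treatment". For between-group comparisons the Statistical analysis plan section names an ANCOVA within a general linear model, "using baseline variables significantly different between groups as covariates, will be used to evaluate the overall difference between groups". That is its only covariate rule; no section names a covariate that will always be in the model.

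Two obvious candidates are available under Research Design. Pharmacodynamic blood sampling is scheduled at "baseline (while patients will be on standard DAPT prior to initiating randomized treatment", so a baseline value of the primary endpoint is planned. Also, "Randomization will be stratified according to type of" P2Y12 inhibitor, so the prasugrel/ticagrelor stratum is known for everyone.

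The same paragraph of the SAP also lists t, Mann-Whitney and Wilcoxon tests for use where appropriate. It does not say which method is primary for the day-30 comparison. Those tests would omit both covariates as well.

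**The concern.** A baseline significance test in a randomized trial asks whether a difference arose by chance, and the answer is known to be yes. It does not say whether the variable predicts the outcome, which is what decides whether adjustment helps. The rule therefore drops a strongly prognostic variable about 95% of the time and lets irrelevant ones in by luck. It works against the stratum in particular, because stratification makes that factor balanced.

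Three things are at stake:

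- The primary model is unknown until the baseline data are seen.
- Standard errors are larger than they need be. The stratum adds to this if MPA differs between prasugrel and ticagrelor patients.
- The test does not run at its nominal 5%. When the screen does not fire, the baseline imbalance is known to be small, yet the unadjusted standard error still allows for a large one. The test is then conservative.

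Precision also bears on the secondary hypothesis that stopping aspirin produces no significant difference, since a less precise test makes that result easier to obtain.

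**Working it through.** **Inputs.** From the sample size section: "Assuming a 10% absolute reduction in CAT-induced MPA with a common standard deviation of 13%, 37 patients per group will be needed", "with a 90% power and 2-sided" alpha of 0.05. Allocation (Research Design): patients are "randomly assigned in a 1:1:1 fashion to one of the following 3 treatment regimens". Significance level (Statistical analysis plan): "A 2-tailed p value of < 0.05 is considered to indicate a statistically significant difference for all the analyses performed". The baseline-to-day-30 correlation r of CAT-induced MPA is not given; 0, 0.3, 0.5 and 0.7 are assumed.

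**1. The plan's own figure.** n = 2(z₀.₉₇₅ + z₀.₉₀)²σ²/δ² = 2 × (1.960 + 1.282)² × 13²/10² = 35.5, so 36 per group. The exact noncentral-t calculation gives 89.6% power at 36 and 90.4% at 37. The stated 37 is reproduced, and it assumes no baseline adjustment.

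**2. How often the rule admits baseline MPA.** By construction of a 0.05 test, 5% of trials. Simulated inclusion was 4.7% to 5.2%.

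**3. What adjustment is worth, by formula.** Residual SD = 13√(1 − r²). The 95% half-width at 37 per group is 1.96 × SD × √(2/37). Required n uses the formula in step 1.

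| r | Residual SD | Half-width (points) | n per group for 90% | t-based power at 37 |
|---|---|---|---|---|
| 0 | 13.00 | 5.92 | 36 | 90.4% |
| 0.3 | 12.40 | 5.65 | 33 | 92.8% |
| 0.5 | 11.26 | 5.13 | 27 | 96.5% |
| 0.7 | 9.28 | 4.23 | 19 | 99.5% |

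**4. The plan's rule against always adjusting.** Simulation of three arms of 37, 20,000 trials per setting. Under the plan's rule, baseline MPA enters only if the three-group baseline ANOVA has p < 0.05.

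| r | Power: rule | Power: always | Mean half-width: rule | Mean half-width: always | Rule wider by | Type I error: rule |
|---|---|---|---|---|---|---|
| 0 | 90.6% | 90.4% | 5.98 | 6.00 | none | 4.9% |
| 0.3 | 91.2% | 93.2% | 5.97 | 5.73 | 4% | 4.8% |
| 0.5 | 91.4% | 96.4% | 5.95 | 5.20 | 14% | 4.4% |
| 0.7 | 91.8% | 99.6% | 5.91 | 4.29 | 38% | 4.0% |

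Always adjusting gave a type I error of 4.8% to 5.0%.

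**5. After the losses the plan expects.** With 146 randomized and 30% lost, 146 × 0.70/3 = 34 per arm remain. With 35% lost, 146 × 0.65/3 = 31.6 remain.

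- At 34 per arm (two-arm simulation, 60,000 trials per cell, baseline t test as the screen), power under the rule vs always adjusting is 87.9% vs 90.1% (r = 0.3), 88.6% vs 94.7% (r = 0.5) and 89.5% vs 99.1% (r = 0.7). Type I error under the rule is 4.8%, 4.4% and 3.7%.
- By formula at 34 per arm, the standard error is 13√(2/34) = 3.15 unadjusted and 3.15 × √0.75 = 2.73 adjusted at r = 0.5.
- At 31 per arm, t-based power is 84.6% unadjusted and 93.1% adjusted at r = 0.5.

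**6. Stratum.** If a share p of patients takes prasugrel and mean MPA differs by d between the two drugs, the unadjusted variance contains p(1 − p)d² that stratification has already removed from the comparison. At the plan's 35% minimum this is 0.35 × 0.65 × d² = 0.2275d². The documents give no d, so only the direction is established.

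**7. Chance entries.** The plan does not list which variables are screened. If there were 20 independent ones (an assumption), at least one would enter by luck with probability 1 − 0.95²⁰ = 64%. Correlated measures would change this figure.

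**The case against.** The trial was sized without adjustment, so at 37 per group the plan's rule still delivers its 90% power, and its error rate is on the safe side. This stands: the loss is relative to a better analysis, not to the target. Power below 90% in step 5 comes from the expected losses, which are a separate matter.

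The size of the loss rests on an unknown r, which could be low. CAT contains TRAP (Description of laboratory assays), and baseline is taken before the PAR-1 inhibitor is started. Baseline may therefore predict day-30 MPA less well on vorapaxar than the single common r used here. This also stands as a limit on size. It does not favour the rule: at r = 0, always adjusting cost 0.2 power points in step 4.

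The most practical objection concerns invalid baseline samples. The plan expects 30-35% invalid results or drop-out, and hemolysis can spoil a baseline sample too. If patients without a valid baseline are dropped, adjustment gains only when the invalid fraction m satisfies (1 − r²)/(1 − m) < 1, that is m < r²: 9% at r = 0.3 and 25% at r = 0.5. In a simulation at 34 per arm, r = 0.3 and an assumed 10% of baselines invalid, complete-case adjustment gave 86.0% power against 87.5% for the plan's rule. The point is fair, but it concerns how the covariate is handled. Filling an invalid baseline with the overall mean, ignoring arm, keeps every patient. The share of variance explained becomes r²(1 − m), here 0.09 × 0.90 = 0.081, so there is still a gain.

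The plan also says its approach follows other pharmacodynamic studies. Precedent does not alter the calculation.

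**Conclusion.** The concern holds. The plan states a covariate rule that omits the baseline of its own primary endpoint in about 95% of trials and almost always omits the stratification factor. Relative to always adjusting at 37 per group, the cost is about 2 power points at r = 0.3, 5 at r = 0.5 and 8 at r = 0.7, and nothing at r = 0. These figures assume a common SD of 13, an effect of 10 points and the same r in each arm. The stratum effect is right in direction but cannot be sized from the documents. The validity of the trial is not threatened, since the test is conservative. What is lost is precision and a primary model fixed in advance. The change should be made, but the trial does not depend on it.

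**What to change.** In the Statistical analysis plan section:

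- Delete the significance-based selection of covariates.
- Name as the primary analysis an ANCOVA of day-30 CAT-induced MPA on treatment arm, baseline CAT-induced MPA and P2Y12 inhibitor (prasugrel or ticagrelor), fitted whatever the observed baseline balance. This also settles the status of the unadjusted tests in the same paragraph.
- State how an invalid or missing baseline value is handled, for example by the overall baseline mean irrespective of arm, so that no patient with a day-30 result is dropped.
- Use the same model, with each assay's own baseline, for the other pharmacodynamic between-group comparisons. Label any further covariates as sensitivity analyses.

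The cost is a sentence or two of text and two degrees of freedom. Both covariates are already part of the planned data, so no extra sampling is needed.

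### The default three-arm linear model shares one residual variance across arms although only one arm stops aspirin; contrasts for thromboxane B2, and possibly the AA-based assays, will have wrong standard errors if that arm's spread differs

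*Combined protocol and SAP*

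**What the plan says.** Patients are randomised 1:1:1 (Research Design) to DAPT plus vorapaxar (arm 1), prasugrel or ticagrelor plus vorapaxar without aspirin (arm 2), or DAPT alone (arm 3). The primary contrast is arm 1 versus arm 3 on CAT-induced maximal platelet aggregation (CAT-MPA) at day 30. The secondary contrast is arm 2 versus arm 1. The other objectives compare all three arms on every pharmacodynamic measure at every time point. Those measures include serum TXB2, AA-induced aggregation and the AA channel of the TEG assay.

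For these comparisons the Statistical analysis plan sets "An analysis of covariance (ANCOVA) method with a general linear model, using baseline variables significantly different between groups as covariates", which "will be used to evaluate the overall difference between groups and all between-groups comparisons, in line with other PD studies". The same section says "Continuous variables will be analyzed for normal distribution with the Kolmogorov-Smirnov test" and "Student's t test, Mann-Whitney U-test and Wilcoxon test will be used to compare continuous variables when appropriate". It does not assign any of these tests to an endpoint or say how they relate to the ANCOVA. It mentions no transformation, no check of equal variance, and no unequal-variance or robust standard error.

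The only SD in the documents belongs to the primary comparison: "Assuming a 10% absolute reduction in CAT-induced MPA with a common standard deviation of 13%, 37 patients per group will be needed".

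**The concern.** A general linear model without further specification estimates one residual variance from all arms in the fit. An overall test across three groups points to a three-arm fit, so arm 2's residuals enter the standard error of every contrast, including arm 1 versus arm 3.

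At baseline this is harmless, because all patients are on aspirin. After randomisation only arm 2 is without it. TXB2 is a concentration from the pathway that aspirin blocks. If its level rises in arm 2, its absolute spread would ordinarily rise too. A common variance then errs in both directions: the vorapaxar effect between the two aspirin arms is judged against too much noise, and the effect of stopping aspirin against too little. The latter is a stated aim of the study. The Kolmogorov-Smirnov test does not guard against this, because it examines distributional shape and not equality of variance.

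**Working it through.** **Reproducing the plan's figure.** Inputs from Study endpoints and sample size calculation: difference 10, SD 13, two-sided 0.05, power 90%. The normal approximation gives 2 × (1.960 + 1.282)² × 13²/10² = 35.5, so 36 per group. The exact t calculation gives power 0.896 at 36 and 0.904 at 37. The stated 37 is confirmed as a two-group calculation; arm 2 plays no part in it.

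**Effect of sharing one variance.** Assume 37 evaluable patients per arm and SDs s, k·s, s in arms 1, 2, 3. The pooled SD is s·√((2+k²)/3). The ratio of model SE to true SE is:

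- arm 1 versus 3: √((2+k²)/3)
- any contrast with arm 2: √(2(2+k²)/(3(1+k²)))

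The type I error of an arm 2 contrast is approximately 2(1 − Φ(1.96 × ratio)).

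| k | SE ratio, arm 1 v 3 | SE ratio, arm 2 contrasts | Type I error, arm 2 contrasts |
|---|---|---|---|
| 1 | 1.00 | 1.00 | 5.0% |
| 1.5 | √(4.25/3) = 1.19 | √(8.5/9.75) = 0.934 | 6.7% |
| 2 | √(6/3) = 1.41 | √(12/15) = 0.894 | 8.0% |
| 5 | √(27/3) = 3.0 | √(54/78) = 0.832 | 10.3% |

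Simulation agrees (8.0% at k = 2, 10.5% at k = 5). The understatement for arm 2 contrasts is capped at a ratio of √(2/3) = 0.816, or about 11% type I error. The overstatement for arm 1 versus 3 has no cap. A Welch test of arm 1 versus arm 2, simulated for k from 0.6 to 3, stays at 4.8% to 5.1%.

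**TXB2 illustration (every input is an assumption).** Log-normal data, 37 per arm, a true two-fold difference between arms 1 and 3. Power for arm 1 versus 3 from the raw-scale three-arm model:

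| Arm 2 median relative to the lower aspirin arm | log-SD 0.8 | log-SD 0.4 |
|---|---|---|
| 2-fold | 81% | 100% |
| 3-fold | 62% | no loss |
| 5-fold | 26% | 99% |
| 10-fold | 1% | 32% |

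At log-SD 0.8 the log-scale analysis has 96% power throughout, and a raw two-arm t test has 88%. In the 10-fold row the raw scale therefore accounts for the drop from 96% to 88%, and the inclusion of arm 2's variance for the drop from 88% to 1%.

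**Primary contrast.** Simulation with SD 13 in arms 1 and 3 and the three-arm pooled variance:

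| Arm 2 SD (k) | Power | Type I error |
|---|---|---|
| 8 (0.62) | 93.8% | 8.0% |
| 10 (0.77) | 93.0% | 6.8% |
| 13 (1.0) | 90.6% | 4.9% |
| 16 (1.23) | 87.6% | 3.4% |
| 19.5 (1.5) | 82.7% | 2.2% |

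At k = 1.2 power is about 88%. By the formula, k = 0.9 gives a ratio of √(2.81/3) = 0.968 and a type I error of about 6%; k = 0.7 gives √(2.49/3) = 0.911 and about 7%. With the variance taken from arms 1 and 3 only, power stays at about 90% and type I error at about 5% whatever arm 2 does.

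**The case against.** The strongest reply is that the problem is conditional and partly inferred.

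- *No arm-level SD is given.* This stands. At k = 1 there is no error, and no value of k can be read from the documents.
- *The plan does not state the measured scale or a single variance.* This also stands. Both are the default reading of an unqualified general linear model, and pairwise contrasts might be refitted on two arms.
- *The plan lists two-sample tests.* In the 10-fold, log-SD 0.8 example, a Kolmogorov-Smirnov test (Lilliefors form) rejects normality in about 89% of single-arm samples, and a Mann-Whitney test of arms 1 and 3 then has about 95% power, nearly that of the log analysis. So the plan contains a route that would avoid the loss. But it is assigned to no endpoint, while the ANCOVA is given all between-group comparisons, so the route cannot be relied on. A rank test also cannot carry covariates, which matters if a baseline variable differs.
- *Study Rationale says prasugrel and ticagrelor also inhibit thromboxane-dependent aggregation.* This weakens the expectation of a large k for AA-induced aggregation. It concerns aggregation and not TXB2 concentration, so the TXB2 argument stands.
- *TXB2 and the AA measures are other objectives.* True; they are neither primary nor secondary, in a study that presents itself as a pilot.

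A reader might also take the width of the TXB2 standard curve, 1000/7.8 = 128-fold, as evidence of skewed data. It is not. It describes the kit's calibration; the protocol says "samples will be diluted with EIA buffer to bring their concentrations within the range of the standard curve", which tells us nothing about spread between patients or arms.

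**Conclusion.** The point holds in conditional form. Under the default reading, standard errors for aspirin-pathway measures will be wrong in both directions if arm 2's spread differs. That is to be expected for TXB2, and less certain for the AA-based assays. For moderate k (1.5 to 2) the arm 1 versus 3 standard error is 19% to 41% too large, and arm 2 contrasts run at about 7% to 8% instead of 5%. The loss for TXB2 could be anything from nil to nearly complete, depending on the size of the shift and the log-SD; the 1% figure is the extreme corner of that range.

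Two stronger readings are tempting and not supported. One is that the intervals for these assays are already known to be invalid; without arm-level SDs that cannot be said. The other is that the primary test has lost its stated power or error rate. Nothing in the documents suggests that arm 2's CAT-MPA SD differs from 13%, and the sponsor hypothesises no significant change in CAT-MPA from stopping aspirin. For k between 0.9 and 1.2 the primary is little affected. What remains there is that the contrast was sized on two arms while the default model draws its error from three. This is a cheap improvement to the plan, not a threat to its main conclusion.

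**What to change.** Amend the Statistical analysis plan as follows:

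1. Analyse TXB2 on the log scale and report geometric mean ratios with confidence intervals.
2. For between-arm contrasts, use arm-specific residual variances or heteroscedasticity-consistent standard errors.
3. Estimate the variance of the primary contrast from arms 1 and 3, the two arms on which it was sized.
4. Fix the scale and the test for each assay in advance, and do not use the Kolmogorov-Smirnov result to choose between tests.

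The cost is a few sentences. If variances are in fact equal, error degrees of freedom for a contrast fall from about 3 × 36 = 108 to 2 × 36 = 72. The 97.5% t quantile moves from 1.982 to 1.993, so intervals widen by about 0.6%. Sample size and data collection do not change.
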